**Covariates.** Covariates will include demographic variables (age in years, education level, marital status, race/ethnicity), tobacco use and cessation history (e.g., average number of cigarettes smoked per day, severity of nicotine dependence, readiness to quit smoking), SHS exposure (smokers in the home), psychosocial measures (depression, anxiety, stress), use of other prescription medications (number), substance use severity (as measured by composite scores in the ASI-Lite), number of recent days of illicit substance use (using ASI for alcohol and other illicit drug use specifically illicit opioids, cocaine, marijuana/THC, benzodiazepines, and methamphetamine), and urine drug test results (positive/negative for marijuana, non-prescribed opioids, benzodiazepines, cocaine, methamphetamine). Covariates will be measured at baseline and at each data collection time-point (with the exception of demographic variables, which are not expected to change) Given the pilot nature of this study and the number of control variables, ability to detect differences in groups may not be possible; however, these data will provide critical information about what baseline demographic, psychosocial and substance use characteristics may be most associated with outcomes.

**Aim 3 Measures:** Using methods described by Drummond and Gold we will assess the reasonableness of the B-EPIC intervention's costs in relation to clinical outcomes achieved and examine the potential for program costs to be offset by reductions in health care utilization. Three types of economic measures will be collected during

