**Power Considerations.** With approximately 50 per group and an alpha level of .05, the power of the two-sample t-test to detect a baseline group difference in a continuous covariate will be at least 84% if the ratio of the difference in means to the standard deviation is at least 0.6. This is slightly larger than a medium effect size. With approximately 50 per group and a .05 level of significance, the power of the chi-square test of association to detect an odds ratio as small as 3.5 will be at least 81%. One way to obtain an odds ratio of this magnitude would be if the prevalence of a given binary covariate at baseline were 60% in one group and 30% in the other. With at least 30 mother/baby dyads completing the study per group and an alpha level of .05, the power of the repeated measures analysis of variance F test to detect a significant main for group will be 79%, assuming a medium effect size, while the power of the F tests to detect a significant main effect of time or group by time interaction will be at least 95%, under these conditions. In the context of repeated measures modeling, a medium effect size is one such that the ratio of the standard deviation of the group means to the standard deviation of the observations within the populations is at least 0.25. Even if this ratio is smaller than a medium

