effect (i.e., 0.20), the power of the repeated measures mixed model will be at least 60% to detect a group effect and 87% to detect a time or interaction effect. While an algorithm for estimating the power associated with a generic GEE model has not been developed, this strategy is analogous to a repeated measures application of logistic modeling. With at least 60 mother/baby dyads completing the study and an alpha level of .05, the power of logistic regression to detect an odds ratio of 2.5 or larger will be at least 68%. While this level of power is not optimal, inclusion of 4 time-points in the GEE models will increase the power of this analysis technique relative to a logistic model for a fixed point in time; this phenomenon is consistent with the comparison of the expected power of a two-sample t-test relative to expected power of a repeated measures comparison of two groups over 4 time-points, namely power for the later exceeds the former under the same conditions. Given the paucity of research regarding tobacco cessation in this at-risk population, it is unknown whether a medium (or slightly smaller) effect size is appropriate for continuous outcomes, such as cigarettes per day. However, in a preliminary study of this population by our group (EMPOWR, described above), we found that 14% of pregnant women decreased their cigarette consumption between intake (typically during the second trimester) and the third trimester. This is notable since each participant chose a health goal to work on (including reducing stress, reducing alcohol/drug use, reducing smoking, or weight management), so not all would have focused on decreasing cigarette consumption. While smoking cessation is the ultimate goal of this intervention, prior research has demonstrated that cutting cigarette consumption below 8 cigarettes per day is a risk reduction strategy for preventing low birthweight, so we will consider outcomes of both successful cessation as well as reduction in consumption for this exploratory project. In addition, a prior study (using a different cessation intervention but with a similar sample size) has demonstrated that while pregnant women addicted to opioids were not able to quit smoking at a higher rate than those not exposed to the intervention, there was a significant increase in readiness to quit, as assessed via stage of change, in the intervention group relative to the controls. We are assessing changes in stage of change over time between the groups for this reason. For all of the inferential tests used in this study, the primary emphasis of these group comparisons will be to estimate effect sizes for the impact of the intervention, which will allow us to estimate power for future (larger) studies. We expect to be able to demonstrate group differences with this exploratory study, given the relatively modest effect sizes required to have a reasonable level of power to detect differences in outcomes between groups. As outlined above, the estimated effect sizes for the longitudinal analyses are expected to be conservative, given that they are based on the minimum expected sample size at the completion of the study; however, since the repeated measures modeling allows for the inclusion of participants who drop out prior to completion, the effective sizes for these group comparisons over time are actually underestimated.

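### The 95% and 87% power for the group-by-time interaction is presented as power for a medium or smaller effect, but it corresponds to a constant follow-up group difference of about 1.15 SD or 0.92 SD

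*Combined protocol and SAP*

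**What the plan says.** The Statistical Analysis Plan analyses continuous outcomes, such as cigarettes per day, with mixed models containing group, time and their interaction over four visits, the first of which is baseline. Allocation is randomised 1:1.

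The repeated-measures part of Power Considerations starts from these conditions: "With at least 30 mother/baby dyads completing the study per group and an alpha level of .05". A medium effect is one whose "ratio of the standard deviation of the group means to the standard deviation of the observations within the populations is at least 0.25". Under that single definition the plan gives 79% power for the group main effect and states that the "power of the F tests to detect a significant main effect of time or group by time interaction will be at least 95" per cent. At a ratio of 0.20 it gives at least 60% for group and "87% to detect a time or interaction effect".

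No within-woman correlation is stated, and the interaction ratio is not translated into a difference between arms at any visit. Earlier in the same section, for a two-sample comparison of baseline covariates, a mean difference of 0.6 SD is described as a little above medium.

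The section calls the project exploratory, says it is not known whether a medium effect is appropriate, and puts the main emphasis on estimating effect sizes. It then concludes: "We expect to be able to demonstrate group differences with this exploratory study, given the relatively modest effect sizes required".

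**The concern.** A ratio of 0.25 means different things for different tests. For a two-group main effect it is a difference of 0.5 SD averaged over visits, which most readers would accept as medium. For a group-by-time interaction it measures how much the group difference varies across visits. A treatment effect that appears after a balanced baseline must be much larger than 0.5 SD to produce that much variation.

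This matters because the expected baseline difference is zero. The interaction is then a natural test for an effect that emerges after randomisation, and it carries the highest power figures in the plan. A reader will take 95% and 87% as the chance of detecting a medium or slightly smaller benefit of B-EPIC, and the closing sentence about modest effects encourages that. The pilot is meant to inform the size of later trials, so a mislabelled effect scale could carry forward.

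The missing correlation adds to the problem, because the two tests respond to it in opposite directions.

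**Working it through.** **Inputs from the plan.** N = 60 (30 completers per arm), m = 4 visits, alpha 0.05, ratio f = 0.25 or 0.20. **Assumed:** equal correlation ρ between all visits (compound symmetry), common SD, zero expected baseline difference.

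**Step 1. Reproduce the plan's figures** (noncentral F).
- Group: λ = N·m·f² / (1 + 3ρ), df 1 and 58.
- Time or interaction: λ = N·m·f² / (1 − ρ), df 3 and 174.
- At ρ = 0.3 and f = 0.25, N·m·f² = 15. Group λ = 15/1.9 = 7.89, power 78.9%. Interaction λ = 15/0.7 = 21.4, power 98.0%.
- At ρ = 0.3 and f = 0.20, N·m·f² = 9.6. Group λ = 5.05, power 59.9%. Interaction λ = 13.7, power 88.2%.

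These agree with the stated 79%, at least 95%, 60% and 87%. At ρ = 0.2 or 0.4 the 79% would become 85% or 73%, so 0.3 is well identified as the working value.

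**Step 2. Translate f into group differences.** Let d_t be the difference between arms at visit t, in SD units. With two equal arms, the interaction f is half the SD of d_t over the four visits, and the group f is half the mean of d_t.
- Sustained effect (0, d, d, d): the mean is 0.75d and the variance is (0.75² + 3 × 0.25²)d²/4 = 0.1875d². So interaction f = 0.433d/2 = 0.2165d.
- f = 0.25 gives d = 0.25/0.2165 = 1.155 SD; f = 0.20 gives d = 0.924 SD. Against 0.6 SD these are 1.9 and 1.5 times as large.
- Linear growth to d at the last visit: f = 0.186d, so d = 1.34 SD or 1.07 SD.
- Any pattern with all d_t between 0 and d: the SD cannot exceed d/2, so f ≤ d/4. The largest difference is then at least 1.0 SD (f = 0.25) or 0.80 SD (f = 0.20). The bound is reached when only two follow-ups differ.
- Group test, sustained effect: f = 0.75d/2 = 0.375d, so f = 0.25 means 0.67 SD at each follow-up.

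**Step 3. Power for a sustained 0.5 SD difference.** With 60 completers, interaction N·m·f² = 240 × 0.10825² = 2.81 and group N·m·f² = 240 × 0.1875² = 8.44. The all-available-data rows use the retention in Table 2 (50, 45, 39 and 28 per arm) with generalised least squares, assuming that women who leave do not return; df are 3 and 218 (interaction), 1 and 98 (group).

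| Data | Test | ρ = 0.3 | ρ = 0.5 | ρ = 0.7 |
|---|---|---|---|---|
| 60 completers | interaction | 35% | 48% | 72% |
| 60 completers | group | 55% | 44% | 37% |
| All available | interaction | 51% | 66% | 87% |
| All available | group | 71% | 61% | 54% |

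**Step 4. Difference needed for 95% interaction power,** sustained, 60 completers: about 1.05, 0.88 and 0.68 SD at ρ = 0.3, 0.5 and 0.7.

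**Step 5. Effect of ρ on the stated group figure.** At f = 0.25 and 60 completers, group power falls from 79% at ρ = 0.3 to 67% at 0.5 and 58% at 0.7, while interaction power rises from 98% to nearly 100%.

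**The case against.** The strongest reply is that nothing has been miscalculated. The stated powers reproduce, the plan defines its ratio openly for repeated-measures models, and the 0.6 SD comparison comes from a different test on baseline covariates. That is right as to the arithmetic. It does not help a reader who takes one label, medium, to mean a similar treatment effect for each test.

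A second reply is that 1.15 SD at every follow-up overstates what is required. This stands. The 1.15 SD figure translates f = 0.25, where power is 98% at correlation 0.3; 95% power needs less (Step 4). Nor does the difference have to be present at every follow-up: two visits at 1.0 SD give the same ratio.

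A third is that the figures for 60 completers are pessimistic, because the planned likelihood analysis uses partial completers. This also stands, which is why both sets are shown. Even with all available data, interaction power for 0.5 SD stays below 95% at each correlation examined.

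A reader might go further and infer that the design cannot show group differences. The documents do not support that. The stated expectation is not tied to the interaction test, and every model also contains a group main effect. With all available data and a sustained 0.6 SD difference, interaction power is about 68%, 83% and 97%, and group power about 85%, 77% and 69%, at correlations 0.3, 0.5 and 0.7. The better of the two tests therefore has at least about 83%.

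**Conclusion.** The point holds as one of labelling and inference. For continuous outcomes, the 95% and 87% interaction powers belong to a constant follow-up difference of about 1.15 SD and 0.92 SD, never below 1.0 SD and 0.80 SD at its largest for same-sign patterns. They are not power for a medium or smaller treatment effect, and the sentence that only modest effects are needed does not follow from them. The figures also depend on a correlation of about 0.3 that the plan does not state.

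This rests on compound symmetry, a common SD, zero expected baseline difference and the inferred correlation. The 0.5 SD benchmark is chosen for illustration: the documents give no SD or expected mean difference, so whether larger effects are realistic cannot be settled from them.

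Two further readings are not supported. The remark under Covariates that the "ability to detect differences in groups may not be possible" is a caveat about the pilot's size and the number of control variables, not a rival power claim, so it does not contradict the plan. Nor do the documents suggest that a null result would be read as evidence against B-EPIC, since the stated emphasis is on estimating effect sizes.

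**What to change.** Revise Power Considerations as follows.

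1. State the within-woman correlation used (0.3 reproduces the figures) and show results at 0.3, 0.5 and 0.7 for both the group and the interaction test.
2. Express the interaction effect as a difference between arms at follow-up, in SD. In place of 95% and 87% for a medium or smaller effect, report both tests for a sustained 0.5 SD difference, for 60 completers and for all available data at Table 2 retention, using the four rows tabulated above. Add the sustained differences that give 95% interaction power with 60 completers.
3. Qualify or remove the sentence that expects group differences because the required effects are relatively modest. The existing statement that the emphasis is on estimating effect sizes can stay.

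The cost is wording only. The stated power becomes less favourable; the sample size, visits and analysis models do not change.

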two study aims will be two-factor (group x time) repeated measures mixed models; these will be estimated using the MIXED procedure or group comparisons of continuous outcomes over time, including cigarette use and tobacco dependence. Generalized estimating equation (GEE), analyses with an exchangeable correlation structure will be used to assess for significant differences between groups and across time for categorical and dichotomous outcomes (e.g., preterm birth, NAS) using the SAS GENMOD procedure. The main effects of group and time and the interaction between them will be included in each model, and covariates will be added to control for group differences. As appropriate, post-hoc pairwise comparisons will be done using Fisher's least significant difference procedure for mixed models and using contrast statements for GEE models.

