**Handling Missing Data.** Based on our prior longitudinal studies with pregnant and postpartum women, we anticipate retention to be at least 60% (9-12% attrition from 2nd-3rd trimester through 1-2 months postpartum; additional 30% attrition to 5-6 month postpartum), as shown in Table 2. The power estimates outlined below are expected to be conservative for several reasons: 1) attrition in the current UKHC MAT program is 12%; 2) we will use escalating and completion incentives to encourage completion; and 3) increased options for follow-up communication (email, text), using each participant's preferred communication method. Maternal and infant outcome data will be extracted from the UKHC medical record and national MEPS, reducing participant burden. Nonetheless, missing data will occur in this vulnerable population and we acknowledge this in the analysis, given that our analysis strategies allow for inclusion of participants who are missing one or more assessments. We will use the intention to treat convention (those randomized to the B-EPIC group will be retained in this group in the analysis whether or not they complete the entirety of the intervention). For the tobacco use indicators, we will examine group differences assuming the last observation carried forward (LOCF; e.g., if a participant is an active smoker at one time-point, we will assume this status at future time-point(s), if she drops out). We will conduct initial analyses using the maximum likelihood approach, as it emphasizes the use of all available data. The use of random effects modeling techniques, including repeated measures mixed modeling, allows for missing data by adjusting the estimation process to account for bias resulting from data missing at random. In addition, multiple imputation will be used as an alternative procedure for handling missing data. Multiple imputation produces results similar to maximum likelihood when used under identical conditions. The strategy of observing differences in group comparisons under these two methods of dealing with missing data is suggested by Hedeker et al. as a way to determine the robustness of the results under these different assumptions. This approach will provide a sensitivity analysis of the group comparisons.

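### The stated 68% power for an odds ratio of 2.5 with 60 dyads is not attainable for B-EPIC versus TAU at one time-point: the ceiling is about 41-43%

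*Combined protocol and SAP*

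**What the plan says.** The Data Analysis part of the SAP assigns dichotomous outcomes, with preterm birth and NAS as examples, to GEE models comparing groups and time-points: "The main effects of group and time and the interaction between them will be included in each model".

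Power Considerations then gives three relevant statements:

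- For a baseline binary covariate with about 50 per group, "the power of the chi-square test of association to detect an odds ratio as small as 3.5 will be at least 81"%. The example is 60% in one group against 30% in the other.
- For the longitudinal analyses, the sample is the expected number of completers: "With at least 30 mother/baby dyads completing the study per group and an alpha level of .05". This fixes the later 60 dyads as a total.
- For binary outcomes with at least 60 dyads and alpha .05, "the power of logistic regression to detect an odds ratio of 2.5 or larger will be at least 68"%. The text concedes that this is not ideal, but says that four time-points will raise the power of GEE "relative to a logistic model for a fixed point in time". The 68% is therefore the single-time starting point.

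The 68% statement gives no predictor, event rate or sidedness. The section later concludes: "We expect to be able to demonstrate group differences with this exploratory study".

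**The concern.** The two binary power statements do not fit together. Moving from the first to the second, the odds ratio falls from 3.5 to 2.5 and the sample from 100 to 60, yet the power falls only from 81% to 68%. Either change alone costs considerable power.

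The figure matters because it is the only one supporting the binary outcomes, including cotinine-verified abstinence under Hypothesis 1. A reader will take 68% as a floor that GEE then lifts. If the true single-time figure is far lower, a null result on abstinence, preterm birth or NAS may be read as evidence of little effect. The misstatement could also carry into planning of the larger trial that this pilot is meant to inform.

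**Working it through.** **Inputs.** Odds ratio 2.5, 60 dyads and alpha .05 (Power Considerations); 30 per group (same section); 1:1 allocation (Randomization); 28 per group at 5-6 months postpartum (Table 2). Two-sided testing is assumed because sidedness is not stated. No control rate is given, so rates from 1% to about 99% were scanned and the maximum taken.

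**Formula.** With control rate p1, the B-EPIC rate is p2 = OR·p1/(1 − p1 + OR·p1). Let d = p2 − p1 and let p̄ be the mean of p1 and p2. Then

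Power = Φ[(d − 1.96·s0)/s1], where s0 = √(2p̄(1 − p̄)/n) and s1 = √((p1(1 − p1) + p2(1 − p2))/n).

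The continuity-corrected version replaces n by n − 2/d + 1/(n·d²).

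**1. Reproduce the plan's 81%.** With n = 50 and 30% v 60%: d = 0.30, s0 = 0.0995, s1 = 0.0949. Power = Φ[(0.30 − 0.1950)/0.0949] = Φ(1.107) = 86.6%. With continuity correction, n becomes 50 − 6.67 + 0.22 = 43.56 and power is 81.5%. The plan's 81% is therefore sound and appears to be the corrected figure.

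**2. Apply the same method to the 68%.** With n = 30 and OR 2.5, power peaks at a control rate near 38.7%, where p2 = 61.2%: d = 0.2251, s0 = 0.1291, s1 = 0.1258. Power = Φ[(0.2251 − 0.2530)/0.1258] = Φ(−0.222) = 41.2%. Exact enumeration of the chi-square test gives 42.6%. The continuity-corrected formula, which reproduced the 81%, gives 31.3%. One-sided testing gives 54.1%.

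**3. Other sample sizes and rates (OR 2.5, two-sided).**

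| n per group | Best rate: normal / exact | Control 10%: normal / exact | Control 5%: normal / exact |
|---|---|---|---|
| 28 | 38.9% / 37.8% | 22.2% / 22.5% | 14.4% / 13.8% |
| 30 | 41.2% / 42.6% | 23.5% / 23.9% | 15.2% / 15.1% |
| 50 | 61.8% / 64.3% | 36.0% / 38.0% | 22.3% / 21.4% |
| 60 | 69.8% / 71.5% | 42.0% / 41.5% | 25.8% / 25.9% |

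The 5% and 10% rates are assumptions for abstinence only. Background Information reports that very few women stopped smoking under a 5A's programme, and TAU is the 5A's approach.

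**4. Cross-check between the two statements.** On the log-odds scale the standardised effect shrinks by (ln 2.5/ln 3.5) × √(60/100) = 0.731 × 0.775 = 0.567. Applied to 81%: Φ(0.567 × 2.838 − 1.96) = 36%. Applied to 86.6%: 41%. Also, with 30 per group, even the larger odds ratio of 3.5 reaches at most 65.9% (normal) to 67.2% (exact). An odds ratio of 2.5 cannot then reach 68%.

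**5. Odds ratio needed for 68% at 30 per group.** About 3.5-3.6 at the best control rate, 5.0-5.1 at 10%, and 6.8-7.4 at 5%.

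**6. Does GEE rescue it?** Treat four equally informative time-points with exchangeable correlation ρ as an effective n of 30 × 4/(1 + 3ρ) per group. At the best rate, power is 72%, 66% and 60% for ρ = 0.3, 0.4 and 0.5. Table 3 labels the first time-point as baseline, so at most three can carry an intervention effect. With 30 × 3/(1 + 2ρ), the figures are 67%, 62% and 57%. Preterm birth and NAS diagnosis occur once and gain nothing.

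**7. What does give about 68%?** One route is 60 per group rather than 60 in total (step 3). Another is a continuous predictor with the odds ratio expressed per SD: Φ[√(60·p(1 − p))·ln 2.5 − 1.96] gives 67.9% at an event rate of 13.5% and 69.2% at 14%. The section does mention 14% ("we found that 14% of pregnant women decreased their cigarette consumption between intake"), but does not link it to this calculation. Neither route is the randomised comparison with 60 dyads in total.

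**The case against.** The arithmetic for 30 per group is not in dispute. The case for leniency has five parts.

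- **The plan is candid about being a pilot.** The Covariates section warns that group differences may not be detectable, and Power Considerations puts its emphasis on effect sizes. This limits the consequence. It does not correct the number, and the same section still expects to show group differences.
- **Sixty is the smallest expected sample.** Preterm birth and NAS come from medical records around delivery, where Table 2 expects 90 women (third trimester) falling to 78 (1-2 months postpartum). The ceiling is 51-53% at 39 per group and 56-57% at 45. For tobacco indicators, "we will examine group differences assuming the last observation carried forward", so up to 50 per group may be analysed. This stands: the best-case shortfall at 50 per group is then 4-6 points rather than 25-27. But 68% is still not reached, and the plan states it for 60 dyads.
- **The 5-10% rates are assumed.** Correct. They should be confined to abstinence, since the Objective section expects NAS in most exposed infants. The 41-43% ceiling does not depend on them.
- **Those low-rate figures are for chi-square, not logistic tests.** Also correct. At 30 per group, exact power at control rates of 10% and 5% is 14% and 2% for the Wald test, and 26% and 20% for the likelihood ratio test, whose type I error can reach 8.9%. No version approaches 68%.
- **The predictor is unnamed.** A continuous predictor could give 68%, and other formulas for that case match at other event rates, so the source of the figure cannot be established. But the sentence is offered as the basis for GEE group comparisons, so it would still need correcting.

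**Conclusion.** The concern holds. Read as the B-EPIC versus TAU comparison at one time-point with 30 per group and two-sided alpha .05, the 68% is overstated by 25-27 points at the most favourable control rate. At assumed control rates of 5-10% the overstatement is 44-53 points. It also conflicts with the section's own 81% when both are read as two-group comparisons.

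The ceiling needs no assumed event rate. It rests on the group-comparison reading, which the context supports although the predictor is not named. No sample size or decision rule depends on the figure, and the continuous-outcome power figures are not challenged here. The point should be fixed because it is a clear error in the only binary power statement.

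**What to change.** 1. Replace the 68% sentence with one that names the predictor, control rate and sidedness. For example: with 30 dyads per group and two-sided alpha .05, power to detect an odds ratio of 2.5 between B-EPIC and TAU at one time-point is at most about 41-43%; for abstinence, at assumed TAU rates of 5-10%, chi-square power is about 15-24%. If a continuous predictor was meant, say so with its event rate, and do not present it as the group comparison.
2. State that outcomes occurring once, such as preterm birth and NAS, gain nothing from repeated time-points, and that even 50 per group gives at most about 62-64%.
3. If a GEE figure is wanted, obtain it by simulation under the planned group, time and interaction model, with stated correlation, control rate and missing-data handling, including LOCF for tobacco indicators.
4. Do not rest the expectation of demonstrating binary group differences on the 68%. Report those outcomes as effect estimates with 95% confidence intervals.
5. Minor: reconcile the 60 dyads and the 60% retention in Handling Missing Data with Table 2, which ends at 56 of 100.

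The cost is SAP wording only, with no added participants or visits; simulation is needed only for item 3. The stated binary power will look less favourable.
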